## 11.6. Study and Site Closure

The sponsor or designee reserves the right to close the study site or terminate the study at any time for any reason at the sole discretion of the sponsor. Study sites will be closed upon study completion. A study site is considered closed when all required documents and study supplies have been collected and a study-site closure visit has been performed.

The investigator may initiate study-site closure at any time, provided there is reasonable cause and sufficient notice is given in advance of the intended termination.

Reasons for the early closure of a study site by the sponsor or investigator may include but are not limited to:

- Failure of the investigator to comply with the Protocol, the requirements of the IRB/IEC or local health authorities, the sponsor's procedures, or GCP guidelines.
- Inadequate recruitment of participants by the investigator.
- Discontinuation of further study treatment development.

# APPENDIX A. INFORMATION REGARDING EFFECTIVENESS OF CONTRACEPTIVE METHODS AND DEFINITIONS

#### **Definitions**

WOCBP: A woman who is considered fertile following menarche and until becoming postmenopausal unless permanently sterile (see below)

Women in the following categories are not considered WOCBP:

- Premenarchal
- Premenopausal with 1 of the following:a
  - Documented hysterectomy
  - Documented bilateral salpingectomy
  - Documented bilateral oophorectomy
- Postmenopausal
  - A postmenopausal state is defined as no menses for 12 months without an alternative medical cause.
    - o A high FSH level in the postmenopausal range may be used to confirm a postmenopausal state in women not using hormonal contraception or HRT. However, in the absence of 12 months of amenorrhea, confirmation with 2 FSH measurements in the postmenopausal range is required.
  - Females on HRT and whose menopausal status is in doubt will be required to use 1 of the nonhormonal, highly effective contraception methods if they wish to continue their HRT during the study. Otherwise, they must discontinue HRT to allow confirmation of postmenopausal status before study enrollment.

#### For male participants of reproductive potentialb

The following methods during the Protocol-defined timeframe in Section 5.1 are highly effective:

- Use of a male condom plus partner use of an additional contraceptive method when having penile-vaginal intercourse with a woman of childbearing potential who is not currently pregnant.
- Vasectomy with medical assessment of the surgical success (verified by site personnel's review of the participant's medical records)
- Sexual abstinencec
- Abstinence from penile-vaginal intercourse

The following are **not** acceptable methods of contraception:

- Periodic abstinence (calendar, symptothermal, postovulation methods), withdrawal (coitus interruptus), spermicides only, and lactational amenorrhoea method.
- Male condom with cap, diaphragm, or sponge with spermicide.
- Male and female condom used together.

Note: Men with a pregnant or breastfeeding partner must agree to remain abstinent from penile-vaginal intercourse or use a male condom during each episode of penile penetration.

#### For female participants who are WOCBP

The following methods during the Protocol-defined timeframe in Section 5.1 that can achieve a failure rate of less than 1% per year when used consistently and correctly are considered as highly effective birth control methods:

- Combined (estrogen and progestogen containing) hormonal contraception associated with inhibition of ovulation.d
  - oral
  - intravaginal
  - transdermal
- Progestogen-only hormonal contraception associated with inhibition of ovulationd
  - oral
  - injectable
  - implantablee
- Intrauterine devicee
- Intrauterine hormone-releasing systeme
- Bilateral tubal occlusione
- Vasectomized partnere,f
- Sexual abstinencec
- a Documentation can come from the site personnel's review of the participant's medical records, medical examination, or medical history interview.
- b If the male participant has a partner with childbearing potential the partner should also use contraceptives.
- c In the context of this guidance, sexual abstinence is considered a highly effective method only if defined as refraining from heterosexual intercourse during the entire period of risk associated with the study treatments. The reliability of sexual abstinence needs to be evaluated in relation to the duration of the clinical study and the preferred and usual lifestyle of the participant.
- d Hormonal contraception may be susceptible to interaction with the investigational medicinal product, which may reduce the efficacy of the contraception method.
- e Contraception methods that in the context of this guidance are considered to have low user dependency.
- f Vasectomized partner is a highly effective method of avoiding pregnancy provided that partner is the sole sexual partner of the WOCBP study participant and that the vasectomized partner has received medical assessment of the surgical success. Source: Clinical Trials Facilitation and Coordination Group (2020).

# APPENDIX B. INSTRUCTION TO PARTICIPANTS FOR HANDLING RUXOLITINIB CREAM

The participant must be instructed in the handling of study cream as follows:

- Store study cream at room temperature.
- Make every effort to apply study cream on schedule.
- Report any missed applications.
- Keep study cream in a safe place and out of reach of children.
- Bring all used and unused study cream tubes to the site at each visit.
- Remove study cream from the tube in fingertip units until all of the areas to be treated are covered by a thin film.
- Do not apply study cream on visit days as it will be applied at the site under supervision of the site staff.
- Do not use more than 1 tube (60 g) per week.
- Emollients, sunscreen, or camouflage makeups should not be used within 2 hours after study cream application.
- Do not apply study cream over sunscreen or camouflage makeup. These must be removed from the skin before application of the study cream. Any makeup remover must then be washed off and the skin dried before application of the study cream.
- Participants should not take baths or showers within 2 hours after study cream application.

# APPENDIX C. COVID-19 PANDEMIC MITIGATION STRATEGIES AND INSTRUCTIONS

The COVID-19 global pandemic presents numerous challenges to the ongoing conduct of clinical trials. In line with the European Medicines Agency Guidelines on the Management of Clinical Trials During the COVID-19 (Coronavirus) Pandemic (2020), the sponsor has issued the following Protocol considerations to ensure participant safety is maintained and adequate benefit/risk analyses are applied relative to the completion of study procedures and maintaining the investigational product supply chain.

Recognizing the flexibility required to manage the impact of the pandemic on this clinical trial, additional details will be added to respective study manuals and project plan documents and communicated to the investigative sites as needed.

## **Study Site Visits**

If local travel restrictions, isolation requirements, or the investigator's benefit/risk assessment determines it to be unsafe for participants to attend study visits at the investigational site, the site staff may elect to pursue the following:

- In order to minimize participant risk, study visits (except Day 1, Week 4, Week 12, and Week 16 visits) may be conducted via telemedicine modalities (phone or video). At a minimum, a review of AEs, concomitant medications, and study drug compliance must be completed. Periodic on-site visits should be conducted whenever feasible. The physician efficacy assessments must not be conducted by phone or video.
- Day 1, Week 4, and Week 16 visits must be conducted in person in their entirety because translational samples and physician efficacy assessments must be conducted in person. Also, the Week 12 visit must be conducted in person, as this is the assessment for possible addition of NB-UVB phototherapy. These visits cannot be missed or conducted remotely. The investigator should document visit-window deviations in the eCRF if necessary. If an out-of-window deviation is significant (ie, > 4 weeks out-of-window), the investigator should contact the sponsor for discussion and further instructions.

## **Investigational Medicinal Product Dispensing and Distribution**

In order to ensure the continuity of providing their participants' clinical supplies within the constraints imparted by the pandemic, the site staff can decide to supply study drug to participants. Adequate supplies of study drug as determined by the investigator can be shipped to the participants by the investigator or appropriately delegated staff (eg, the study pharmacy staff) using a third-party service if duly authorized by the participant. The study site may use their own preferred courier, provided the courier adheres to certain standards (eg, use of personal protection equipment, maintenance of temperature-controlled transit environment), or one centrally contracted by the sponsor.

## **Clinical Trial Monitoring**

Study monitoring visits may be postponed; however, the site monitor will continue to employ off-site monitoring practices such as routine communication methods (eg, phone calls, emails,

video visits) with the sites to get information on trial progress, participant status, and information on issue resolution. The study monitor may remotely review data entered into the EDC for accuracy and completeness. Remote source data verification may be implemented with agreement of the principal investigator and institution, as applicable.

If the study-site monitor cannot be on-site to perform the final drug accountability for reconciliation purposes, and the operation cannot be postponed, it may be performed by a pharmacist from the hospital pharmacy or by the study coordinator/data manager with suitable training. The study drug can be returned to the sponsor by the hospital pharmacy directly, or it can be destroyed in accordance with local practices, if applicable, and with sponsor approval.

# APPENDIX D. WHO CLASSIFICATION OF TOPICAL CORTICOSTEROIDS

Hydrocortisone and betamethasone are examples of low- and high-potency topical corticosteroids. Topical corticosteroids have been ranked in terms of potency into 4 groups consisting of 7 classes. Class I topical corticosteroids are the most potent, and Class VII are the least potent. Efficacy and side effects are greatest with the Class I ultra-high-potency preparations, which should only be used for limited time periods (2-3 weeks). Representative preparations by group are listed in the table below. These groups may vary depending on the formulation and concentration and should be considered approximate. In general, ointments are more potent than creams or lotions. Potency is also increased when topical corticosteroids are used under occlusive dressings or in intertriginous areas.

[figure not shown]
Potency	Class	Topical Corticosteroid	Formulation
Ultra high	I	Clobetasol propionate	Cream, 0.05%
		Diflorasone diacetate	Ointment, 0.05%
High	II	Amcinonide	Ointment, 0.1%
		Betamethasone dipropionate	Ointment, 0.05%
		Desoximetasone	Cream or ointment, 0.025%
		Fluocinonide	Cream, ointment or gel, 0.05%
		Halcinonide	Cream, 0.1%
	III	Betamethasone dipropionate	Cream, 0.05%
		Betamethasone valerate	Ointment, 0.1%
		Diflorasone diacetate	Cream, 0.05%
		Triamcinolone acetonide	Ointment, 0.1%
Moderate	IV	Desoximetasone	Cream, 0.05%
		Fluocinolone acetonide	Ointment, 0.025%
		Fludroxycortide	Ointment, 0.05%
		Hydrocortisone valerate	Ointment, 0.2%
		Triamcinolone acetonide	Cream, 0.1%
	V	Betamethasone dipropionate	Lotion, 0.02%
		Betamethasone valerate	Cream, 0.1%
		Fluocinolone acetonide	Cream, 0.025%
		Fludroxycortide	Cream, 0.05%
		Hydrocortisone butyrate	Cream, 0.1%
		Hydrocortisone valerate	Cream, 0.2%
		Triamcinolone acetonide	Lotion, 0.1%
Low	VI	Betamethasone valerate	Lotion, 0.05%
		Desonide	Cream, 0.05%
		Fluocinolone acetonide	Solution, 0.01%
	VII	Dexamethasone sodium phosphate	Cream, 0.1%
		Hydrocortisone acetate	Cream, 1%
		Methylprednisolone acetate	Cream, 0.25%

Source: WHO 1997.

# APPENDIX E. PROTOCOL AMENDMENT SUMMARY OF CHANGES

Not applicable.

1. INTRODUCTION

This is an open-label study in which participants will apply ruxolitinib 1.5% cream BID to all depigmented areas (ie, up to 10% BSA) for up to 48 weeks. Participants will continue to treat depigmented areas identified for treatment at baseline regardless of whether the area begins to improve or fully repigment.

On Day 1, all participants will apply ruxolitinib 1.5% cream BID as monotherapy. At Week 12, participants will apply ruxolitinib 1.5% cream alone or in combination with NB-UVB, the latter of which is based on improvement in T-VASI score. Participants who have < T-VASI25 will have NB-UVB phototherapy added to their ruxolitinib 1.5% cream BID regimen (Group A); this team will be given NB-UVB phototherapy 3 times per week through Week 48 (ie, 36 weeks). Participants who have \ge T-VASI25 at Week 12 will continue on-treatment with ruxolitinib 1.5% cream BID alone (Group B).

Following the last application of ruxolitinib 1.5% cream alone or in combination with NB-UVB at Week 48, there will be a 30-day safety follow-up period.

The purpose of this SAP is to provide details of the statistical analyses that have been outlined in the INCB 18424-217 Protocol. The scope of this plan will be executed by the Department of Biostatistics or designee, and the analyses of PK and PD will be executed by the Department of Clinical Pharmacokinetics or designee in this SAP.

2. STUDY INFORMATION, OBJECTIVES, AND ENDPOINTS

2.1. Protocol and Case Report Form Version

This SAP is based on INCB 18424-217 Protocol dated 30 SEP 2021 and CRF approved 18 FEB 2022. Unless superseded by an amendment, this SAP will be effective for all subsequent Protocol Amendments and CRF versions.

3. STUDY DESIGN

This is an open-label study in which participants will apply ruxolitinib 1.5% cream BID to all depigmented areas (up to 10% BSA) for up to 48 weeks. Participants will continue to treat depigmented areas identified for treatment at baseline regardless of whether the area begins to improve or fully repigment.

On Day 1, all participants will apply ruxolitinib 1.5% cream BID as monotherapy (see Figure 1). At Week 12, participants will apply ruxolitinib 1.5% cream BID alone or in combination with NB-UVB based on their T-VASI score. Participants who have < T-VASI25 will have NB-UVB phototherapy added to their ruxolitinib 1.5% cream BID regimen (Group A). The NB-UVB phototherapy will be given 3 times per week through Week 48 (ie, 36 weeks). Participants who have \ge T-VASI25 at Week 12 will continue on ruxolitinib 1.5% cream BID alone (Group B).

The study schema is shown below in Figure 1. All participants will have follow-up assessments 30 (+7) days after the last application of study drug.

Figure 1: Study Design Schema

3.1. Randomization

Not applicable.

3.2. Control of Type I Error

All statistical analyses for efficacy endpoints are exploratory in nature. No alpha control will be implemented. Unless otherwise specified, all CIs provided will be at the 95% confidence level.

3.3. Sample Size Considerations

Due to the exploratory nature of the study, the sample size is not based on calculation of statistical power. The sample size is considered to be sufficient to obtain adequate efficacy, safety, tolerability, and PK data to achieve the objectives of the study.

Approximately 50 participants will receive ruxolitinib 1.5% cream BID for 12 weeks. At Week 12, participants will be assigned to ruxolitinib cream 1.5% BID alone or in combination with NB-UVB phototherapy based on their T-VASI score.

3.4. Schedule of Assessments

Refer to the Protocol dated 30 SEP 2021 for a full description of all study procedures and assessment schedules for this study.

4. DATA HANDLING DEFINITIONS AND CONVENTIONS

4.1. Scheduled Study Evaluations and Study Periods

4.1.1. Day 1

Day 1 is the date that the first application of ruxolitinib cream is administered to participants in the specific period.

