#### 4. STUDY DESIGN

### 4.1. Overall Design

This is an open-label study in which participants will apply ruxolitinib 1.5% cream BID to all depigmented areas up to 10% BSA for up to 48 weeks. Participants should continue to treat depigmented areas identified for treatment at baseline regardless of whether the area begins to improve or fully repigment.

On Day 1, all participants will apply ruxolitinib 1.5% cream BID as monotherapy (see Figure 1). At Week 12, participants will apply ruxolitinib 1.5% cream alone or in combination with NB-UVB based on improvement in T-VASI score. Participants who have < T-VASI25 will have NB-UVB phototherapy added to their ruxolitinib 1.5% cream BID regimen (Group A). NB-UVB will be given 3 times per week through Week 48 (36 weeks). Participants who have  $\geq$  T-VASI25 at Week 12 will continue on ruxolitinib 1.5% cream BID alone (Group B). For participants who receive combination therapy, NB-UVB machines will be supplied by the sponsor for at home use during the study.

At any time during the study, if vitiligo areas become significantly more extensive than from the previous visit, the participant should contact the study site to discuss with the investigator whether additional evaluation at the clinic is required. Participants who have expansion of areas of vitiligo identified at baseline or new areas of vitiligo during the course of the treatment period should not treat the additional areas of vitiligo with ruxolitinib cream.

Participants who permanently discontinue NB-UVB will be allowed to remain in the study and continue to apply ruxolitinib 1.5% cream BID alone. Participants who permanently discontinue ruxolitinib 1.5% cream BID will be allowed to remain in the study and continue NB-UVB phototherapy alone.

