4.1.2. Study Day

If a visit/reporting date is on or after Day 1, then the study day at the visit/reporting date will be calculated as follows:

Day # = (visit/reporting date - Day 1 date + 1).

If the visit/reporting date is before Day 1, then the study day at the visit/reporting date will be calculated as follows:

Day # = (visit/reporting date - Day 1 date).

A study day of -1 indicates 1 day before Day 1.

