5.2. Treatment Groups

This is an open-label study composed of a 48-week treatment period, including a 12-week treatment run-in. During the 12-week run-in, all participants will apply ruxolitinib 1.5% cream BID. Following these 12 weeks, participants will receive either ruxolitinib 1.5% cream BID alone or ruxolitinib 1.5% cream BID plus NB-UVB phototherapy for 36 weeks. Participant groups were determined based on their T-VASI score at Week 12. Data will be summarized based on the treatments that the participant received.

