6.5. Study Drug Compliance

For the participants in the FAS population, overall compliance (%) for the application of ruxolitinib cream during the treatment period will be calculated for all participants as follows:

Compliance (%) of ruxolitinib cream = $100 \times [\text{total number of applied applications}] / [\text{total number of prescribed applications}].$

The total number of intended applications is the number of planned applications minus the number of interrupted applications.

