9.2. Adverse Events

9.2.1. Adverse Event Definitions

A TEAE is any AE either reported for the first time or worsening of a pre-existing event after first application of study drug and within 30 days of the last application of study drug. For participants who have NB-UVB phototherapy added, the first application date is period-specific, and the end date is 30 days after the last application date in this period, or the day before the first application date in the next period, whichever comes first. Analysis of AEs (as discussed below) will be limited to TEAEs, but data listings will include all AEs regardless of their timing in relation to study drug application.

Adverse events will be tabulated by MedDRA PT and SOC. Severity of AEs will be graded using the NCI CTCAE v5. The CTCAE reporting guidelines and grading details are available on the Cancer Therapy Evaluation Program website.

The subset of AEs considered by the investigator to be related to study drug will be considered to be treatment-related AEs. If the investigator does not specify the relationship of the AE to study drug, the AE will be considered to be treatment-related. The incidence of AEs and treatment-related AEs will be tabulated. Serious AEs will also be tabulated.

Any missing onset date, causality, or severity must be queried for resolution. Unresolved missing causality and severity will be handled according to the following rules:

- An unresolved missing causality will be considered treatment-related.
- An unresolved missing severity will be identified as an unknown severity.

For purposes of analysis, all AEs will be considered TEAEs unless the AE can unequivocally be defined as not treatment-emergent.

Application site reactions are AEs that occur at the site of drug application. A summary of ASRs will be provided.

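### The SAP anchors its period-specific Day 1 and TEAE window to a cream application and never defines the periods, so Group A's combination window can open before the first NB-UVB session

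*SAP*

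**What the plan says.** SAP 4.1.1 gives the time origin: "Day 1 is the date that the first application of ruxolitinib cream is administered to participants in the specific period". SAP 4.1.2 counts study day from that date.

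SAP 9.2.1 carries the idea into the safety analysis: "For participants who have NB-UVB phototherapy added, the first application date is period-specific". A period's window closes 30 days after the last application in it or on "the day before the first application date in the next period, whichever comes first".

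Application, in the SAP, means cream. SAP 6.5 defines "overall compliance (%) for the application of ruxolitinib cream during the treatment period", while SAP 6.6 treats NB-UVB separately, in sessions and days of machine use. Nowhere does the SAP name the first NB-UVB session as the start of anything.

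The nearest thing to a definition of the periods is SAP 5.2, after its description of the 12-week run-in: "Following these 12 weeks, participants will receive either ruxolitinib 1.5% cream BID alone or ruxolitinib 1.5% cream BID plus NB-UVB phototherapy for 36 weeks". It names no event or date that opens the second part. The same section says that data are summarized by treatment received.

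Two other places use a single origin. SAP 1 says "On Day 1, all participants will apply ruxolitinib 1.5% cream BID as monotherapy", and SAP 3 repeats this. SAP 4.1.3 ties baseline to the first cream application, with no reference to a period.

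On delivery, Protocol 4.1 says of Group A that "NB-UVB machines will be supplied by the sponsor for at home use during the study". Protocol 6.1 has cream applied in the clinic on visit days and, for combination therapy, at least 2 hours before phototherapy.

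**The concern.** Splitting the TEAE window only for participants who have NB-UVB added makes sense if the aim is to separate AEs on the combination from AEs on cream alone. A cream anchor cannot do that. Cream is twice daily with no planned break at Week 12, so the first application of a second period is not a distinct event in the data. A programmer has to pick a date, and the obvious pick is the supervised application at the Week 12 visit.

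That application comes before the first NB-UVB session, which takes place at home. The two schedule tables have no row for device handover or first session, and NB-UVB first appears in them as a compliance check at Week 16. Any AE in between arises on cream alone but falls in the combination window. This sits poorly with the as-treated rule in SAP 5.2.

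At stake is which AEs are counted under the secondary objective on safety and tolerability of the combination. The study has about 50 participants and no randomized control, so moving a few between summaries is visible. There is also an internal conflict over study day.

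**Working it through.** **Planned NB-UVB period.** Week 12 through Week 48 is 48 − 12 = 36 weeks, as Protocol 4.1 and the SAP state. A full 36 weeks requires the first session at about Week 12.

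**Where the combination window opens.**
1. SAP 9.2.1 starts it at a period-specific first application.
2. By SAP 6.5 and 6.6, an application is of cream.
3. SAP 5.2 places the second part directly after the 12-week run-in.
4. Protocol Table 3 and Protocol 6.1 put a supervised cream application at the Week 12 visit.
5. The literal start is therefore that application. The first session follows after a gap, g, that the documents do not give.

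**Illustrative size.** The inputs are:
- About 50 participants (SAP 3.3).
- 21.2% reached T-VASI25 at Week 12 on 1.5% BID in Study INCB 18424-211 (Protocol 2.4).
- 67.2% on active treatment, all regimens pooled, had at least one TEAE in that study's 24-week vehicle-controlled period (Protocol 2.3).
- g is assumed to lie between 0 and 4 weeks.

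Expected Group A size: 50 × (1 − 0.212) = 39.4.

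Weekly AE rate, taken as constant: −ln(1 − 0.672) / 24 = 0.0464.

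Participants with at least one AE in the gap: 39.4 × (1 − exp(−0.0464 × g)).

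| Assumed gap | Participants with an AE in the gap |
|---|---|
| none | 0 |
| 3 days | 0.8 |
| 1 week | 1.8 |
| 2 weeks | 3.5 |
| 4 weeks | 6.7 |

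These counts are a ceiling for the change in the any-TEAE line. A participant with an AE in the gap may have another after NB-UVB starts and would then be counted either way.

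**Study day.** SAP 4.1.2 takes the visit date minus the Day 1 date, plus one. With nominal visits at day 7 × week + 1:

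| Visit | From first-ever cream application | If Day 1 restarts at Week 12 |
|---|---|---|
| Week 12 | 85 | 1 |
| Week 16 | 113 | 29 |
| Week 48 | 337 | 253 |

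The shift is 84 days. SAP 4.1.1 is not limited to Group A, so if Weeks 12 to 48 form a period, Group B restarts as well. Only the TEAE rule in SAP 9.2.1 is limited to participants with NB-UVB added.

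**The case against.** The strongest reply is that SAP 4.1.1 defines Day 1 within a period and does not say what opens the period. If adding NB-UVB opens it, the first cream application in it falls at about the time of the first session, and the AE problem largely disappears. That reading is possible. The SAP does not state it, and SAP 5.2 points instead to Week 12. So the firm defect is an undefined boundary with a cream-only anchor.

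The second reply is that no delay is documented. Protocol 2.6 plans combination therapy from Week 12, and the Week 16 PK note in Table 4 refers to participants starting the combination at Week 12. A missing schedule row does not show a delay. This stands: the gap is an assumption and its range must include zero.

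A reader might also infer four stronger things that the documents do not support:
- **A Week 12 baseline for the primary endpoint.** SAP 4.1.3 is not period-specific, and the laboratory baseline in SAP 9.3.1 also uses the first application.
- **Diluted exposure-adjusted AE rates.** None are planned. SAP 9.2.2 lists numbers and percentages of participants.
- **Cream events attributed to NB-UVB.** Relatedness is the investigator's judgement, and the window describes cream plus NB-UVB. It affects which summary an AE enters.
- **A study-day restart in Group A alone, as settled fact.** The SAP does not state a restart, the wording would reach both groups, and SAP 1 and 3 contradict it. Efficacy is summarized by visit, so no planned result is shown to change.

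**Conclusion.** The point holds, and it is minor. The SAP names an anchor that cannot identify the start of the combination while cream is continuous, and it does not define the periods that the anchor depends on. On the literal reading, AEs between the Week 12 application and the first NB-UVB session are tabulated as combination TEAEs although only cream had been used.

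The size ranges from about 0 participants with no gap to about 2 to 7 of roughly 39 in Group A for gaps of 1 to 4 weeks. That rests on an assumed gap, a responder rate carried over from the earlier study, and a constant AE rate taken from pooled active regimens in that study.

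The period-specific Day 1 also contradicts the single Day 1 in SAP 1 and 3. Neither issue touches baseline or the Week 48 change in T-VASI, and the study is descriptive, with no formal tests.

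**What to change.** In the SAP:
1. Define the periods and the event that opens each one.
2. Use one Day 1, the first-ever cream application, for study day in both groups.
3. Start the Group A combination TEAE window at the first NB-UVB session recorded by the device. Count AEs before that date under cream alone.
4. State that Group A participants who never start NB-UVB stay in the cream-alone safety summary.

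The cost is a few SAP sentences and one derived date. Under Protocol 6.4 the machine already records sessions and site staff must document treatment dates, so no new data are needed.
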